Guided by the CFIR,⁴² we conducted semi-structured interviews with 16 providers from 10 practices to systematically identify barriers to HPV vaccination in pediatric practices.⁴⁷ This investigation revealed that all providers were aware of the CDC recommendations for HPV vaccination and universally assumed responsibility for vaccine delivery. Typically, for both girls and boys, providers recommended the HPV vaccine at the 11-12-year-old check-up visit. All but one provider used an explanatory style for this discussion, and the strength of their recommendation varied. All reported that persuading hesitant parents to vaccinate was difficult and time consuming; some delayed these discussions until the child was older and the parents were more accepting. Teamwork to deliver the vaccine series was uncommon, and no providers were aware of their partners' approach to HPV vaccination or monitored vaccine coverage.

Using 2014 data, we found that vaccine initiation and completion by age 13 varied among providers from 2% to 26%, and 1% to 26%, respectively, and varied 4 to 5-fold among providers within the same practice. These data demonstrate the urgent need for changes in vaccine delivery in community-based practices in our community to increase optimal use of this vaccine. By comparing factors between providers with higher and lower HPV vaccine coverage, we identified¹⁴ CFIR constructs across all five domains of the conceptual framework that were important barriers to following CDC guidelines.⁴⁸ Most distinguishing factors related to provider characteristics – their lack of buy-in to vaccination by age 13, their lack of confidence to address parental hesitancy, and poor communication skills to promote timely HPV vaccine use. Coverage was higher in practices with coordination between the provider and staff to ensure opportunities for vaccination were not missed. As described in our recent publication,⁴⁷ we crafted an implementation strategy (the intervention) to address these factors, guided by the TDF.^{43, 46} The intervention was further developed during a practice quality improvement project, described below.

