4 STUDY DESIGN

4.1 OVERALL DESIGN

We will complete a single site, cluster-randomized trial to evaluate the effectiveness of a multi-component implementation strategy (the intervention) to increase use of the HPV vaccine according to CDC guidelines. Randomization will occur after baseline assessment and the unit of randomization is a community-based, primary care pediatric practice. The randomization schema will be generated and implemented by the study statistician. Twenty practices will be randomized into two groups, the 2-year intervention group (n=10) or a wait-list control group (n=10). The intervention includes: 1) an educational video to increase the provider's knowledge about guideline recommendations and patient and practice benefits of vaccination by age 13; 2) audit and feedback of vaccine coverage to increase motivation to engage in practice change; 3) a communication strategy to improve the provider's communication skills and their self-efficacy to address parental hesitation; and 4) practice facilitation to support practice change to develop a sustainable HPV vaccine delivery system. The intervention will be delivered through a series of brief practice visits with the facilitator that occur every 1-4 weeks over 2 years. Vaccine use will be assessed at the practice level using 12-months of routinely collected clinical data to allow for seasonal variation in care delivery patterns. Vaccine use will be assessed at baseline, at 12 and 24 months to assess effectiveness, and at 36 months to assess if change is sustained. Due to the 2020 pandemic and overall concerns for safety, we will use ZOOM video conferencing for research activities, including obtaining measures and implantation of the intervention

The study hypotheses are: 1) *The 2-year intervention will increase the percentage of preteens who receive HPV vaccine before their 13th birthday by at least 13 percentage points, and benefits will be sustained at 36 months.* 2) *The intervention will increase on-time HPV vaccination by increasing providers' capability (communication skills) and their motivation (confidence in their capabilities) to deliver on-time HPV vaccination.*

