5.5 STRATEGIES FOR RECRUITMENT AND RETENTION

Practices: We will invite all potentially eligible practices that are affiliated with WU PAARC and Community Outpatient Practice Experience (COPE) to participate. The first 20 practices that agree to participate will be randomly assigned to the intervention or control group using an allocation ratio 1:1.

Practices may be contacted by email, fax, letter, phone, or in-person to invite participation. All providers in the practice will be invited to participate. [name] and/ or a member of the study team will meet with those who are interested in learning more about the study to explain the details of study participation and answer any questions. These meetings will be held at the provider's office. If we experience difficulty with recruitment, we may expand our criteria to include solo practitioners and practices who still maintain paper records, as well as practices in the community that are not affiliated with WU PAARC or COPE.

We anticipate that we will recruit ~80 primary care pediatricians from the 20 participating practices. We estimate the racial/ethnic breakdown of participating physicians based on surveys completed by members of our PBRN, the available study population. We estimate that 27% of participating physicians will be male, ~84% will be Caucasian, 6% African American, 7% Asian. About 6% will be Hispanic. Due to the 2020 Coronavirus pandemic, the baseline parent survey was eliminated. Changes in EMR protocols has made parent contact information inaccessible, therefore the electronic parent survey has been completely eliminated from the study. The goal of this survey, to assess if parental satisfaction with HPV vaccine care differed between study groups, will be met by adding questions to the provider survey. Specifically, to assess provider experiences with patient complaints and loss to the practice related to HPV vaccine delivery, repeating the measure from the baseline provider survey.

Incentives: We will provide financial compensation for time taken to participate in the study including \$500/year for the business entity of each participating practice for administrative expenses (obtaining the lists of eligible patients, allowing study team access to medical records, etc.). We will also provide \$50 for providers who complete study surveys.

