6.3 MEASURES TO MINIMIZE BIAS: RANDOMIZATION AND BLINDING

Bias: Although most providers will be from St Louis metropolitan area, they will be drawn from the bi-state area. We will gather information to describe participants and eligible non-participants to assess selection bias and allow others to assess the relevance of our findings to their situation.

Randomization: We will stratify practices into 2-groups by the number of providers. (≤ 4 and ≥ 5) We will randomize within the strata using a block design.

Blinding: It is not possible to blind investigators or practices from group assignment. The RA and the data analyst will be blinded to group assignment and are responsible for assessment of the primary and secondary outcome measures of HPV vaccine use. Blinding is not necessary for baseline measurements as this will occur prior to randomization. Thus, baseline measures may be completed by other members of the study team. In addition, measurement bias will be minimized for the assessment of these outcomes by using a standardized approach for data collection and analysis, as well as quality checks.

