8 STUDY ASSESSMENTS AND PROCEDURES

8.1 ENDPOINT AND OTHER NON-SAFETY ASSESSMENTS

Mixed methods of data collection will be used including audit of the electronic medical record (EMR) to extract routinely collected and previously recorded data, surveys, and field notes. The study team will follow the same measurement procedures for both study groups.

The primary and secondary outcomes (vaccine initiation and completion by age 13, respectively) will be assessed by audit of the EMR, completed by the research assistant (RA) and/or a member of the study team. To assess variation among providers in the same practice, we will sample records from each participating provider. Measurement will be completed over four 12-month time periods (baseline, 12, 24, and 36 months). For each measurement period, the physician's office will provide an electronic list of eligible patients with an office visit with each participating provider. For each practice, a member of the study team will randomly select a sample of 60 records per provider from this list for review by the RA and or other member of the study team. As much as possible the number of records will be balanced across providers. Data abstracted from the record will include date and type of index visit (well child, acute care, and other e.g., immunization), date of birth, date of vaccination for HPV vaccine, Tdap, and MCV, sex, race/ethnicity and insurance status. Records will be de-identified for patient, provider and practice identifiers, and given a unique subject ID number.

Providers: At baseline and at 12- and 24-months, in addition to the EMR audit described above, all participating providers will complete a brief survey to assess their knowledge, attitudes and behaviors regarding HPV vaccination. The baseline survey will also assess demographic and other practices and physician-level factors that may affect intervention success and are needed to describe the study sample. The practice facilitator will keep detailed field notes about practice observations, contextual factors and practice change components, and will monitor the implementation process.

Practices: At baseline, the project coordinator and/or a member of the study team will meet with the practice manager to complete a brief practice survey to describe the practice and current HPV vaccination procedures. HPV vaccination procedures will be reassessed in a similar manner at 12- and 24- months.

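### Baseline HPV initiation is audited before practices are randomised, yet neither the allocation nor primary model (1) uses it; the cost is precision, and credibility if the arms differ by chance

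*Combined protocol and SAP*

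**What the plan says.** - **Timing.** Section 4.1: "Randomization will occur after baseline assessment and the unit of randomization is a community-based, primary care pediatric practice". Section 6.3 agrees: "Blinding is not necessary for baseline measurements as this will occur prior to randomization". Sections 1.3 and 8.1 place an EMR audit of vaccine initiation and completion at baseline as well as at 12, 24 and 36 months. Sections 1.1 and 6.1.1 say that baseline rates are given to all providers.
- **Allocation.** Section 6.3: "We will stratify practices into 2-groups by the number of providers", cut at 4 or fewer against 5 or more, and then "We will randomize within the strata using a block design". Section 5.5: "The first 20 practices that agree to participate will be randomly assigned to the intervention or control group using an allocation ratio 1:1". No matching, stratification or constraint on baseline coverage is described.
- **Primary analysis.** Model (1) in 9.4.2 contains a treatment indicator and random intercepts for practice and provider, and uses Year 2 data. It has no baseline-coverage term and no size-stratum term.
- **Baseline rate as a covariate.** Sections 9.4.2, 9.4.7 and 9.4.9 list it among examples of covariates that may be added in secondary or exploratory analysis.
- **Expectation.** Section 9.2 expects the two arms to start from a similar initiation rate.
- **Spread.** Section 2.2 reports, from 2014 data, that initiation and completion by age 13 "varied 4 to 5-fold among providers within the same practice".

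**The concern.** The strongest available predictor of the 24-month outcome is likely to be the same outcome measured at baseline, and it is in hand when practices are allocated. The plan balances provider count instead, and no section links provider count to coverage. With 10 practices per arm and large differences between providers, the arms can start several points apart by chance. The primary model then compares Year 2 proportions without reference to the starting point.

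Two things are at stake. The first is precision: stable provider differences stay in the error of the comparison although the data to remove them are collected. The second is credibility. If the baseline table shows a gap of 5 points, over a third of the 13-point target, readers will ask how much of the result was there at the start. An optional adjustment chosen after the data are seen is a weak answer.

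**Working it through.** **Inputs.** Section 9.2 gives practice variance 0.01 and provider variance 0.75² = 0.5625 (logit scale), rates 0.40 and 0.53, 95 providers recruited (47.5 per arm) and 60 charts per provider. The practice size mix (2 to 8 providers, total 95) is assumed, using the range in the amendment history.

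**1. The plan's own figure.** A simulation of the three-level logistic model with 4 providers × 30 children per practice, 10 + 10 practices and two-sided 0.05 gives power 0.84 by likelihood-ratio test and 0.82 by t-test on practice means. This agrees with the stated power of over 0.80. It takes 0.40 and 0.53 as population proportions; read as values for a median provider, they give 0.75.

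**2. Variances on the probability scale at 0.40** (numerical integration).
- Provider: Vb ≈ 0.0260.
- Practice: Va ≈ 0.00046.
- Within provider: Vw = 0.40 × 0.60 − 0.0260 − 0.0005 = 0.2135.

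**3. SD of the observed baseline gap.**
Var = 2 × [Va/10 + Vb/47.5 + Vw/(47.5 × 60)]
= 2 × [0.000046 + 0.000548 + 0.000075] = 0.00134, so SD ≈ 3.7 points.
P(|gap| > 5) ≈ 17% by the normal distribution, and 8.6% in a given direction. Simulated size-stratified allocation gives 17.1%, against 17.5% without strata, so the size strata hardly help.

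**4. Sensitivity to the documents' other counts** (rate 0.40).

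| Providers | Charts each | SD (points) | P(gap > 5) |
|---|---|---|---|
| 80 | 30 | 4.2 | 23.2% |
| 80 | 60 | 4.0 | 20.7% |
| 95 | 30 | 3.9 | 19.5% |
| 95 | 60 | 3.7 | 17.2% |
| 120 | 60 | 3.3 | 12.8% |
| 120 | true gap, no sampling error | 3.1 | 10.6% |

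The range is roughly 1 in 4 to 1 in 9. At a baseline rate of 0.5 with 95 providers and 60 charts it is 18.6%.

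**5. Carry-over to 24 months.** Part of the observed gap is sampling error. The true-gap SD is 3.45 points, so the true share of the variance is 3.45²/3.66² ≈ 0.89. Expected carry-over is persistence × 0.89, where persistence is the correlation of provider effects between baseline and Year 2. The documents do not give it. At 0.5, 0.7 and 0.9 this is 0.44, 0.62 and 0.80 points per point; simulation gives 0.43, 0.62 and 0.79. At persistence 0 it is 0. A 5-point gap therefore moves the unadjusted estimate by about 2.2 (0.43 × 5) to 4.0 (0.79 × 5) points.

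**6. Error rates.** Over all randomisations the unadjusted test keeps type I error near 5%. Among only those trials with an observed gap above 5 points, its false-positive rate is 9%, 16% and 19% at persistence 0.5, 0.7 and 0.9, against about 5% after baseline adjustment.

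**7. Gain from adjustment.** The reliability of a provider's baseline rate is 0.0260/(0.0260 + 0.2135/60) ≈ 0.88. Adjusted SD ≈ 3.66 × √(1 − (0.88 × persistence)²):
- 0.5: 3.66 × √(1 − 0.194) ≈ 3.3
- 0.7: 3.66 × √(1 − 0.379) ≈ 2.9
- 0.9: 3.66 × √(1 − 0.627) ≈ 2.2 (simulation: 2.3)

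In a practice-level analysis with 80 providers and 60 children each, power for 13 points is 0.85 to 0.86 unadjusted. Adjusted, it is 0.83, 0.86, 0.90, 0.96 and above 0.99 at persistence 0, 0.3, 0.5, 0.7 and 0.9.

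**8. Gain from constrained allocation.** Drawing at random from the best-balanced 20% of size-stratified 10:10 allocations cuts the true-gap SD from about 3.5 to 1.3 points (1.7 with 30 baseline charts). The observed-gap SD falls further, to about 0.6, because allocations are selected on it; the true gap is what carries forward. Once the model is adjusted, the added precision at persistence 0.7 is about 2.9 to 2.8, which is near simulation error.

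**The case against.** The best defence is that the design is valid as it stands. Randomisation makes the unadjusted comparison unbiased, the random effects put between-provider variance into the standard error, and the stated power already allows for it. Stratifying by size has its own stated purpose in amendment 1.04 and is a legitimate choice where practices range from 2 to 8 providers. The baseline rate is named as a possible covariate. The documents give no persistence figure, so the benefit is uncertain, and at persistence 0 adjustment loses a little power (0.83 against 0.85 to 0.86). The increase to 60 charts per provider is dated January 2022, so the baseline audit may have used fewer. All of this stands, and it limits the point to efficiency and pre-specification.

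A reader might infer more, and the documents do not support it:
- **That the trial is biased or its overall type I error inflated.** It is not; the higher false-positive rates in step 6 apply only to trials that happen to have a large gap.
- **That the whole gap passes into the result.** Carry-over is partial and rests on an assumed persistence. The within-practice spread in 2.2 also partly averages out.
- **That nothing in the plan could address a gap.** The optional secondary covariate could; it is simply neither primary nor committed.
- **That block allocation lets an unblinded team predict assignments.** Section 4.1 assigns both creating and applying the schema to the study statistician, block size is not stated, and the documents do not say whether practices are allocated one by one or together.

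**Conclusion.** The point holds as a missed, nearly free gain in precision and a gap in pre-specification. An observed baseline difference above 5 points in either direction has a chance of about 17% with 95 providers and 60 charts each (about 1 in 12 in a given direction; roughly 1 in 4 to 1 in 9 across the documents' other counts). This rests on the plan's own variances and an assumed size mix. What reaches month 24 is about 0.4 to 0.8 of the gap at persistence 0.5 to 0.9, so a 5-point gap would account for some 2 to 4 points of the 13-point target. The random intercepts keep the test valid on average, but they do not remove a particular imbalance. Nearly all the attainable precision comes from the analysis model; balancing the allocation as well mainly protects the appearance of the baseline table.

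**What to change.** **Section 9.4.2.** Move baseline initiation rate from the optional secondary covariates into primary model (1), together with the size stratum used in randomisation. State whether the rate is at practice or provider level and, if provider level, what is used for a provider without a baseline audit. Keep the unadjusted model as a sensitivity analysis, and report the baseline gap between arms. Make the change before any outcome is analysed by arm. It costs one paragraph and no new data; the only statistical price is the small loss of power if persistence is near zero.

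**Section 6.3, only if practices are not yet allocated.** The documents do not say; the amendment history runs to August 2022, so allocation may be complete. If it is still open, keep the two size strata, list the 10:10 allocations, retain those with a small between-arm difference in baseline initiation, and have the study statistician draw one at random. Fix the retention rule in advance. This costs a short program, and practices must wait for the slowest baseline audit in their batch. If allocation is complete, the change to 9.4.2 is enough.

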4.2 SCIENTIFIC RATIONALE FOR STUDY DESIGN

A rigorous evaluation such as the proposed cluster randomized controlled trial is needed to establish the effectiveness of the intervention in a generalizable sample prior to scaling for widespread use. Randomization will be at the level of the practice for two reasons: 1) the intervention is designed to change the system for adolescent vaccine delivery at the practice level, and 2) to prevent contamination of provider behavior within the same practice. The 3-year follow-up required for assessment of sustained change, a key consideration prior to widespread dissemination, precluded a stepped wedge design.

Practices will be recruited from community pediatric practices in the St. Louis metropolitan area and are representative of independent practices where vaccination typically occurs. Our sample size of 20 practices (~80 providers) allows us to test the primary hypothesis and provide interpretable results. All providers (intervention and control groups) will receive information provided by the CDC to assist motivated providers who want to improve use of HPV vaccine that are representative of “usual care.” These will include the current recommendations, background information and the CDC’s patient educational materials and website. The wait-list control group will be offered the intervention after the evaluative study is completed. Initiation of HPV vaccine by age 13 is the primary outcome as local providers suggested this is the most difficult barrier to overcome to achieve optimal use of this effective vaccine. Vaccine outcomes will be assessed at the clinic level using 12-months of routinely collected clinical data to allow for seasonal variation in care delivery patterns (the majority of check-up visits occur in the summer). This measurement approach is characteristic of quality metrics and is needed to show change in vaccine coverage over time, as the guidelines are age-specific. The outcome assessor will be blinded to study group allocation to minimize measurement bias.

4.3 JUSTIFICATION FOR INTERVENTION

The reasons for under-use and sub-optimal use of HPV vaccine are complex and require an innovative solution. A systematic assessment of the HPV vaccination process identified that the barriers to use were related to provider and practice characteristics. We developed a multi-component intervention designed to simultaneously address all these factors. Previous research has shown that interventions to change physician behavior are most effective if they are based on national guidelines, address specific barriers to change, and include several components.^{49,50} The proposed intervention is based on CDC guidelines, addresses specific barriers to HPV vaccine use in primary care practices, and has multiple components. It is informed by the Theoretical Domain Framework, a behavioral change theory specific for primary care providers, and has been refined by pilot testing. It is designed for sustainability, using practice facilitation to support practice change, allowing 2 years for sustained change to occur. Preliminary testing suggest the intervention is effective, acceptable to providers and ready for community-level testing.

4.4 END-OF-STUDY DEFINITION

Intervention practices are considered to have completed the study after the baseline, 12-, 24- and 36-month measurements for vaccine coverage have been collected. Control practices may continue for an additional 24 months to receive the intervention.

5 STUDY POPULATION

5.1 INCLUSION CRITERIA

IN ADDITION TO PROVIDING APPROPRIATE CONSENT, PRACTICES AND INDIVIDUALS MUST MEET THE FOLLOWING INCLUSION CRITERIA TO PARTICIPATE IN THE STUDY. FOR EACH GROUP OF STUDY SUBJECTS, PARTICIPATION IS OPEN TO ALL, INCLUDING ANY GENDER AND RACIAL AND ETHNIC GROUP.

Practice	Providers	Adolescents
Community-based pediatric primary care practices with 2 or more providers	Providers who deliver wellness care to preteens and adolescents	Adolescents 10-13 years of age during the measurement period
Practice in St. Louis metropolitan area	Willingness to complete study questionnaires	At least one visit during the measurement period
Willingness to participate in the practice facilitator-guided QI process	Willingness to participate in the practice facilitator-guided QI process	

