1 PROTOCOL SUMMARY

1.1 SYNOPSIS

Title:	Randomized Controlled Trial to Evaluate an Implementation Strategy to Increase Optimal Use of HPV Vaccine in Primary Care		
Grant Number:	R01CA2356515-01A1		
Study Description:	We will complete a cluster-randomized trial to evaluate the effectiveness of a multi-component implementation strategy (the intervention) to increase use of the HPV vaccine according to CDC guidelines. Twenty community pediatric practices will be randomly assigned to the intervention or wait-list control condition.		
Objectives*:			
	Primary Objective:	Compare, at 24 months, the proportion of eligible preteens who receive 1st dose (primary endpoint) and 2nd dose (secondary endpoint) of HPV vaccine before their 13th birthday in practices that receive the intervention with practices in the wait-list control group.	
	Secondary Objectives:	Compare these outcomes at 36 months to assess the sustainability of intervention benefit.	
		Determine whether the intervention effect on vaccination outcomes is mediated by providers' increased belief in their capabilities to provide on-time HPV vaccination (primary outcome) and by their increased use of a presumptive, announcement approach to recommend HPV vaccine (secondary outcome)	
		Explore if the intervention effect on vaccination outcomes is mediated by the degree of practice change as measured on an 18-item HPV vaccine delivery score.	
		Assess the implementation fidelity, the acceptability and appropriateness of the intervention for providers, parental satisfaction with care, and cost.	

Endpoints*:	Primary Endpoint: The proportion of eligible preteens who receive the 1st dose of HPV vaccine before their 13th birthday at 24 months post randomization. The proportion of eligible preteens who receive the 2nd dose of HPV vaccine before their 13th birthday at 24 months post randomization.
Secondary Endpoint:	The proportion of eligible preteens who receive the 1st dose of HPV vaccine before their 13th birthday at 36 months post randomization.
	The proportion of eligible preteens who receive the 2nd dose of HPV vaccine before their 13th birthday at 36 months post randomization.
Study Population:	Approximately 120 Community based pediatric primary care providers in the St. Louis metropolitan area , who work in the 20 participating practices
Phase* or Stage:	3 (Low-risk behavioral intervention)
Description of Sites/Facilities Enrolling Participants:	The study will be conducted at Washington University

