9.3 POPULATIONS FOR ANALYSES

Data analyses will adhere to the intention-to-treat principle, allowing 12-months grace period to implement practice changes. The primary analysis will compare the overall proportion of eligible preteens who initiated and completed HPV vaccination in the intervention and control practices at 24 months, using Year 2 measurements for vaccine use. Maintenance of change will be assessed using Year 3 measurements.

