9.4.2 ANALYSIS OF THE PRIMARY ENDPOINT(S)

Data analyses will adhere to the intention-to-treat principle, allowing 12-months grace period to implement practice changes. The primary analysis will compare the overall proportion of eligible preteens who initiated and completed HPV vaccination in the intervention and control practices at 24 months, using Year 2 measurements for vaccine use. Maintenance of change will be assessed using Year 3 measurements. The analytic approach is to use a multi-level random effects logistic model to account for the hierarchical structure: children clustered within providers clustered within practices.

Define by y_{ijk} as the binary variable of HPV vaccine for the k th child of provider j of practice i . There are 3 hierarchical levels: children clustered within providers clustered within practices. We use random effects to capture the intra-class correlation at the provider and the practice levels. We assume a multi-level random effects logistic model (a generalized linear mixed model):

$$\text{logit } P(y_{ijk}=1) = \beta_0 + trt_{ijk}\beta_1 + a_i + b_{ij} \quad (1)$$

[figure not shown]
where trt_{ijk} is the treatment indicator for practice i , and β_1 is the treatment effect. We use random effects a_i and b_{ij} to describe heterogeneity in the practice level and provider level, and assume $a_i \sim N(0, \sigma_a^2)$ and $b_{ij} \sim N(0, \sigma_b^2)$ are independent. The practice level random intercept is used to accommodate extra-variation in outcome measurements due to clustering of providers in a practice, and the provider level random intercept is used to accommodate extra-variation in outcome measurements due to clustering of individual patients within a provider.

As secondary analysis, we can add other covariates in the model, e.g., gender, category of practice (urban vs. rural), vaccine rate at baseline for a provider or practice, etc. Interaction of treatment and these covariates can be included in the model to study the moderating effect of these risk factors. The interaction of random effects (both at the practice and provider levels) and covariates can be added in the model as well.

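### The endpoint is a dose before the 13th birthday, but unless the sample is restricted, the 10-13 age rule and a model without age give on-time vaccination to date in a mixed-age group

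*Combined protocol and SAP*

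**What the plan says.** Section 1.1 gives the primary endpoint as "The proportion of eligible preteens who receive the 1st dose of HPV vaccine before their 13th birthday at 24 months post randomization". Section 3 repeats this for initiation and completion, at 24 and 36 months.

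Section 5.1 sets two conditions for patients: "Adolescents 10-13 years of age during the measurement period", and a visit in that period. Section 8.1 says "Measurement will be completed over four 12-month time periods" and that a team member "will randomly select a sample of 60 records per provider from this list". The abstracted items include the index visit date and "date of birth, date of vaccination for HPV vaccine, Tdap, and MCV".

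Section 9.4.2 introduces the outcome only "as the binary variable of HPV vaccine for the" *k*th child of a provider. Model (1) has an intercept, a treatment term and random intercepts for practice and provider. The optional covariates in 9.4.2, 9.4.7 and 9.4.9 do not name age, although the list is open-ended. Section 9.3 uses Year 2 measurements, "allowing 12-months grace period to implement practice changes".

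Section 4.2 defends the 12-month cross-sectional measure as "needed to show change in vaccine coverage over time, as the guidelines are age-specific". The schema in 1.2 is not visible in the available text; the amendment history shows that it described measurement of preteens.

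**The concern.** A dose before the 13th birthday is a settled outcome only once the child has been dosed or has turned 13. A random draw from children aged 10 to 13 includes many who are neither. The visible text does not say when age is taken, whether 13 ends at 13.0 or 13.99, on what date a chart is read, or how an undosed child still under 13 is scored.

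Three things are at stake:
- **The level.** The printed proportion depends on the age mix and the reading date.
- **The contrast.** A practice that gives the same doses sooner shows more vaccinated 11- and 12-year-olds, even if coverage at 13 is unchanged. The endpoint as named would call that no effect.
- **Completion.** It is affected more, because section 6.1.2 says the series takes 6 to 12 months.

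**Working it through.** **1. The plan's own figures.** The ICC in 9.2 reproduces: 0.75²/(0.75² + π²/3) = 0.5625/3.852 = 0.146, stated as 0.15. So does power over 0.80: simulating model (1) with 10 practices per arm, 4 providers and 30 children gives 0.85 (1,000 runs) when 0.40 and 0.53 are marginal proportions. This takes 0.40 as given and does not show which age group it describes.

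**2. Age at period end.** The documents give no age distribution, so this is an assumption. Age at visit A is uniform on 10.0-13.99 or 10.0-13.0, the visit is uniform over the 12 months, and age at period end is X = A + U with U uniform on (0,1).

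| | 10.0-13.99 | 10.0-13.0 |
|---|---|---|
| Under 13 at period end | (3 − 0.5)/4 = 62.5% | (3 − 0.5)/3 = 83% |
| Turned 13 in the period | 25% | 17% |
| Turned 13 before it | 12.5% | 0% |

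X has density 1/4 (or 1/3) between ages 11 and 13.

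**3. Printed level when true by-13 coverage is 40%.** Two assumed uptake curves set the limits.
- All doses at 11.0: the share already dosed is 0.875 or 0.833, and 0.40 times this is 35% or 33%.
- Doses spread evenly over ages 11-13: the share is 1/4 × 1 + 0.375 = 0.625, or 1/3 × 1 + 0.167 = 0.50, which prints 25% or 20%.

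The reading date matters too. With even spread and status read at the visit, the shares are 0.50 and 0.333, which print 20% and 13%.

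For completion, put dose 2 at 6 to 12 months (uniform) after dose 1. With uptake starting at age 11, 38-69% of by-13 completions are dated by period end, against 50-88% of initiations.

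**4. Timing only.** Both arms reach 40% at 13. Control doses are even over 11-13; intervention doses are even over 11-12.5 (3 months earlier on average) or 11-12 (6 months earlier). The difference is 0.40 × density × the area between the curves.
- *New timing from randomisation.* Every child under 13 at month 24 turned 11 after randomisation. The areas are 0.25 and 0.50, giving +2.5/+3.3 points (3 months) and +5.0/+6.7 points (6 months) for 10.0-13.99/10.0-13.0.
- *New timing only for children turning 11 after month 12.* Only ages 11-12 at month 24 count. The areas are 0.5 × (1/1.5 − 1/2) = 0.083 and 0.5 × (1 − 1/2) = 0.25, giving 0.8/1.1 and 2.5/3.3 points.
- *Children who turn 13 in the period.* The difference is zero.

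An age term alone does not remove this. At exactly age 12, control shows 0.40 × 0.5 = 20%, and the 3-month shift shows 0.40 × 1/1.5 = 26.7%.

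**5. Limits of the turn-13 group.** Let u be the years since the 13th birthday at month 24; the child was then 11 + u at randomisation. With even uptake, the share of control doses before randomisation is the mean of u/2: 25% (u uniform) or 17% (density 2(1 − u), the 10.0-13.0 reading).

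For the contrast, take constant yearly hazards over ages 11-13 that give 0.40 and 0.53 under full exposure: −ln(0.60)/2 = 0.255 and −ln(0.47)/2 = 0.378, a gap of 0.122. Intervention coverage is 1 − 0.47·exp(0.122u) if the effect starts at randomisation, and 1 − 0.60·exp(−0.122(1 − u)) if it starts at month 12. Averaging over u:

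| Effect starts | Turn-13 group, 10.0-13.99 / 10.0-13.0 | Whole 10-13 sample |
|---|---|---|
| Randomisation | 10.0 / 11.0 points | 7.1 / 7.2 |
| Month 12 | 3.5 / 4.7 points | 4.1 / about 5 |

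**6. Precision.** The turn-13 group holds 0.25 × 60 = 15 or 0.167 × 60 = 10 charts per provider. The plan's variance components on the probability scale are, for practice, provider and child, 0.0005, 0.0260, 0.2135 at 0.40 and 0.0005, 0.0277, 0.2209 at 0.53. With 10 practices and 47.5 providers per arm, SE² sums practice/10 + provider/47.5 + child/(47.5m) over the arms. With t(18) = 2.10, the 95% half-width is 7.8, 9.0 and 9.7 points at m = 60, 15 and 10.

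**The case against.** The 12-month cross-sectional measure is deliberate and usual for quality metrics. Randomisation balances age on average. Silence on scoring is not a rule that an undosed child under 13 counts as a failure, and the schema may settle it. The pilot in 2.2 sampled ages 11.0-13.0 and found 62% before intervention, which suggests the team has a to-date metric in mind. The word preteen favours an upper limit at 13.0.

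Much of this stands. The design is not in dispute, and the text does give a calendar anchor. But that anchor is not a status date for each child, and under the 10.0-13.0 reading more children are still under 13, not fewer. If a to-date metric is intended, the endpoint's description has to say so. The sizes rest on assumed ages and curves, and the 62% shows that actual levels may be quite different.

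A reader might infer more than the documents support:
- **That the trial is underpowered.** This depends on what 0.4 describes. Section 9.2 says only national data. The figure is close to the 39% for 13-year-olds in 2.1 and 2.2, but if it already describes the mixed group, the stated power is untouched.
- **That the primary test is invalid.** The age rule is the same in both arms, so the test is valid for the null of no effect on timing or coverage. It is not a test of by-13 coverage alone.
- **That children who turn 13 should replace the sample.** They turned 11 before randomisation, and with a delayed effect their contrast is the smaller one (3.5 against 4.1, or 4.7 against about 5).

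**Conclusion.** The concern holds on the text. The endpoint is a by-13 outcome, and the stated denominator and model give coverage to date in a mixed-age group unless the sample is restricted in a way the visible text does not state. The estimate would not be the named quantity, and it could register earlier dosing as higher coverage. The illustrated sizes show that the gap can be material but do not predict it; they change with the age distribution, the uptake curve and the start of the effect. It should be fixed before any comparison by arm.

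**What to change.** State the following in 5.1, 8.1, 9.3 and 9.4.2, in agreement with the schema, before any comparison by arm:

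1. The date at which age is taken, the upper age limit (13.0 or 13.99), and period end as the status date in all four measurement periods, counting only doses before the 13th birthday.
2. The 10-13 analysis is kept, with age at the status date (capped at 13) added to model (1), and its result labelled on-time vaccination to date. The age term handles the age mix; it does not turn the result into by-13 coverage.
3. Beside it, the by-13 proportion for initiation and completion in sampled children whose 13th birthday falls in the period, with the number of counted doses dated before randomisation shown by arm.

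In 9.2, say which age group the 0.4 describes.

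The cost is wording, one covariate and one table; birth, visit and dose dates are already abstracted. The drawback lies in item 3: it uses roughly a quarter or a sixth of the charts, has the wider intervals shown above, and includes exposure before randomisation. It should be read beside the 10-13 result, not in place of it.
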